## **9. Data Collection**

### **9.1. Retention of documentation**

The Principal Investigator (PI) will retain all copies of the records relating to the study for a minimum period of 5 years from the completion or discontinuation of the study. In all cases, the Principal Investigator (PI) must contact the Study Sponsor prior to disposing of any records related to the study. Included in records to be maintained are signed Protocol, copies of the Case Report Forms, signed consent forms, IRB approval letters, correspondence concerning the clinical study and any other documents to identify the subjects.

In addition, if the Principal Investigator (PI) moves/retires, etc., they should provide *Solvay Dental 360™* with the name and address of the person who will look after and be responsible for the study related records.

### **9.2. Site Qualification / Selection**

Principal Investigator's (PI) and investigation sites will be selected by the Sponsor or Sponsor's representative through the Principal Investigator and site qualification process. All selected Investigators will be responsible for complying with all study-related and regulatory requirements and will be ultimately responsible for overseeing the conduct of the study at their respective investigation sites, per the Investigation Agreement.

Selected Principal Investigators (PIs) will have the required training and expertise to conduct the study. The investigation sites where assessments are to be performed must have the adequate volume of the target subject population, experienced staff, as well as the appropriate facilities and equipment to meet the requirements of the study protocol and the expected enrollment time frames.

All Principal Investigators (PIs) and research staff must be willing to undergo all study related training and participate and assist with monitoring initiated by the Sponsor or Sponsor's representative.

## 10. Termination of the Study

### 10.1. Subject Withdrawals and Discontinuation

During the course of this study, subjects will be or may elect to withdraw from further treatment through any of the following reasons:

- Subject's rescission of consent.
- Any unexpected adverse device effect which is, in the opinion of the Principal Investigator, related to the device and will endanger the well-being of the subject if the treatment is continued.
- The development of any undercurrent illness(es), infection or condition(s) that might interfere with the Protocol.
- Any problem deemed by the Principal Investigator (PI) and/or Solvay Dental 360™ to be sufficient to cause discontinuation.

All subjects discontinued from the study due to an unexpected adverse device effect, directly related to the study, will be treated until the effect resolves. The Principal Investigator (PI) will clearly document the date and reason(s) for subject withdrawal in his/her Case Report Form and the monitor must be notified.

Subjects who are withdrawn will not be replaced if they have received the investigational device. If possible, any procedures or assessments planned for the subject on withdrawal from the study should be performed when intention to withdraw the subject is announced.

Subjects who are withdrawn prior to receiving investigation device will be replaced.

### 10.2. Early Termination of the Clinical Investigation

Both the Sponsor and the Principal investigator (PI) reserve the right to terminate the clinical investigation at any time. Should this be necessary, the procedures will be arranged on an individual basis after review and consultation by both parties. In terminating the clinical investigation Solvay Dental 360™ and the Principal investigator (PI) will assure that adequate consideration is given to the protection of the subject's interests.

## 11. Data Management

Electronic case report forms (eCRF) via a web-based Electronic Data Capture (EDC) system will be utilised for the study. The eCRF will be completed for each included patient. The completed eCRFs will not be made available in any form to third parties without written permission from Data Management. The data will be reviewed by Data Management, monitor or designee and queries will be issued. The study site personnel are required to resolve any such queries. At the end of the study, Data Management will perform final validation checks, including central consistency checks, after which Clean File will be declared and the database locked.

## 12. Statistics

This section provides a summary of the planned statistical analyses.

### 12.1. Description of Statistical Methods

#### 12.1.1. General Statistical Considerations

The primary endpoint will be the difference in the overall score from the Oral Health Impact Profile (OHIP-14) questionnaire between baseline (assessing the metal RPD) and follow-up (assessing the polymer RPD). This overall score for each frame is calculated by a summation of the score from each of the 14 questions; each having the following scoring:

Response	Score
Never	0 Points
Hardly Ever	1 Point
Occasionally	2 Points
Fairly Often	3 Points
Very Often	4 Points

Thus the range of possible scores for the overall score is 0 to 56.

The overall score from the questionnaire provided at baseline to assess the cobalt chrome frame will be subtracted from the overall score obtained at 8 weeks follow-up when assessing the polymer frame. This difference that is calculated, along with other continuous variables will be summarized using the mean, median, standard deviation, and inter-quartile range. A one-sample t-test will be used to test the difference in the overall scores against a performance goal.

Change from baseline will be calculated by subtracting the overall score of the cobalt chrome frame from the overall score of the polymer frame. The mean change will be used to assess the hypothesis. A one sample t-test against a performance goal will be conducted with the following hypothesis:

$$H_0: OS_{\text{diff}} > \Delta$$

$$H_a: OS_{\text{diff}} \leq \Delta;$$

Where  $OS_{\text{diff}}$  is the overall score for the cobalt chrome frame subtracted from the overall score for the polymer frame, and  $\Delta$  is the performance goal. The performance goal is 1.5.

### 12.1.2. Study Cohorts for Analyses

Because this is a prospective observational study, all subjects with available questionnaire data at both baseline and follow-up will be included in the study cohort for analysis.

### 12.1.3. Primary Outcome

The primary endpoint will be the difference in the overall score from the Oral Health related Quality of Life questionnaire between baseline and follow-up. This score is calculated by a summation of the score from each question; each having the following scoring:

Response	Score
Never	0 Points
Hardly Ever	1 Point
Occasionally	2 Points
Fairly Often	3 Points
Very Often	4 Points

A non-inferiority test will be conducted with the following hypothesis:

$$\begin{aligned} H_0: OS_{\text{diff}} &> \Delta \\ H_a: OS_{\text{diff}} &\leq \Delta; \end{aligned}$$

Where  $OS_{\text{diff}}$  is the overall score for the cobalt chrome frame subtracted from the overall score for the polymer frame, and  $\Delta$  is the performance goal. The performance goal is 1.5.

### 12.1.4. Secondary Outcomes

Plaque score and gingival bleeding index are considered secondary endpoints and will be summarised at both baseline and follow-up. In addition, framework hygiene (disclosing), BOP, probing depths, abutment teeth mobility and health of the RPD mucosal bearing areas, as well as professional (operator) based outcomes of the function, occlusion and aesthetics are important outcomes. Additionally, the denture preference will be summarised and considered a secondary endpoint for the study as well.

### 12.1.5. Poolability Analyses

Poolability analyses will be performed on the primary endpoint to assess whether results are poolable across the participating centers.

A linear regression model with change in the summary score of the Oral Health related Quality of Life Questionnaire as the dependent variable will be reported using a categorical variable for site. If there is evidence that the data is not poolable across centers, examination of the data will be performed to determine the underlying cause(s).

### 12.1.6. Missing Data

It is anticipated that missing data will be very minimal. Every effort will be made to collect complete data from all patients. In the event of missing data, the extent and types of missing data will be assessed and reported.

## 12.2. Sample Size Determination

In a previous study (S. Shaghaghian, 2014), the average overall score on the OHIP questionnaire for subjects wearing a cobalt chrome denture was 13.8 (standard deviation = 10.1). Based on the anticipated improved performance of the polymer frame, 36 subjects with an alpha level of 0.05 provides approximately 80% power to detect a difference of -3 (standard deviation = 11) between the 2 overall scores with a non-inferiority margin of 1.5. The total number of subjects enrolled will be 40, given the anticipated attrition rate of 10%.

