No formal hypothesis testing will be done for the secondary endpoints.

8. Trial Success Criteria

Success of the primary endpoints will be based on a significance level of $\alpha = 0.05$. That is, if the hypothesis test results in a p-value that is less than 0.05, the study will be considered a success.

9. Trial Design

This is a multi-center, cohort study conducted in the United States and United Kingdom that will enroll approximately 40 subjects to assess Oral Health Related Quality of Life (OHRQoL) in patients receiving the study polymer Removable Partial Denture (RPD) as compared to their baseline Cobalt Chrome (CoCr) Removable Partial Denture (RPD) Oral Health Related Quality of Life (OHRQoL).

Subjects who are current wearers of a Cobalt Chrome (CoCr) Removable Partial Denture (RPD) will complete an Oral Health Related Quality of Life (OHRQoL) instrument, the Oral Health Impact Profile (OHIP) questionnaire, at baseline and again after wearing their prescribed polymer Removable Partial Denture (RPD) for 8 weeks.

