9.2 Blinding

Blinding will not be used in this study.

10. Sample Size Considerations

Power calculations of the non-inferiority of the overall score on the OHIP questionnaire for subjects wearing a polymer frame versus the overall score on the OHIP questionnaire for subjects wearing a cobalt chrome denture were based on a non-inferiority test for one mean where higher means are worse and $\alpha=0.05$.

In a previous study (S. Shaghaghian, 2014), the average overall score on the OHIP questionnaire for subjects wearing a cobalt chrome denture was 13.8 (standard deviation = 10.1). Based on the anticipated improved performance of the polymer frame, 36 subjects provides approximately 80% power to detect a difference of -3 (standard deviation = 11) between the 2 overall scores with a non-inferiority margin of 1.5. The total number of subjects enrolled will be 40, given the anticipated attrition rate of 10%.

11. Data Structure and Handling

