12.5.1.2 Hypothesis and/or parameters to be estimated

The primary endpoint analysis will be performed on all subjects with an overall score reported on the OHIP questionnaire for both the Cobalt Chrome and Polymer Frame. The objective of the primary analysis is to show non-inferiority of the difference in the overall score of the OHIP questionnaire after using the CoCr removable partial denture and after using the polymer RPD to a performance goal of 1.5. The hypothesis will be tested, and can be written as follows:

$H_0: OS_{diff} > \Delta$ versus

$H_A: OS_{diff} \leq \Delta$,

where

- OS_{diff} is the overall score for the cobalt chrome frame subtracted from the overall score for the polymer frame
- Δ is the performance goal

The statistical analysis of the non-inferiority of the difference in the overall score from the OHIP for each frame to a performance goal of 1.5 will be done using the PROC TTEST procedure in SAS.

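### Does leaving alpha 0.05 without a stated side make the success rule ambiguous or the claimed power of about 80% wrong?

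*Protocol*

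**What the plan says.** The sample size statement is in Protocol 12.2: "36 subjects with an alpha level of 0.05 provides approximately 80% power to detect a difference of -3 (standard deviation = 11", with a margin of 1.5 and 40 enrolled to allow for 10% attrition. SAP section 10 repeats the figures and adds that the calculation was "based on a non-inferiority test for one mean where higher means are worse".

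The hypotheses appear four times, in Protocol 12.1.1 and 12.1.3 and in SAP sections 7 and 12.5.1.2, always in the same direction. The null is that the mean difference (polymer minus cobalt chrome) exceeds the performance goal. The alternative is that it is at or below the goal. The goal is 1.5 and the test is a one-sample t-test.

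SAP section 8 gives the success rule: "if the hypothesis test results in a p-value that is less than 0.05, the study will be considered a success". SAP 12.5.1.2 says that the analysis "will be done using the PROC TTEST procedure in SAS". No section uses the words one-sided or two-sided, gives a sides option, or states a confidence level.

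**The concern.** Two things look wrong at first.

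- **Power.** A reader who computes exact t-test power from the stated inputs gets less than 80%, and a reader who takes 0.05 as two-sided gets a great deal less. The sample size then seems too small for its claim.
- **Decision rule.** SAP section 8 asks only for a p-value below 0.05. Read alone, it does not say which p-value. If the analyst could choose between a one-sided and a two-sided value after seeing the data, some results would pass under one and fail under the other. Taken literally with a two-sided p-value, the sentence would even count a mean significantly worse than +1.5 as success.

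This is the trial's only formal test of an endpoint, in an unblinded single-arm study, so a real ambiguity here would matter.

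**Working it through.** **Inputs** (Protocol 12.2 and SAP section 10): evaluable n = 36; assumed difference −3; SD of the difference 11; margin 1.5; alpha 0.05; attrition 10%. The test, from Protocol 12.1.1, is a one-sample t-test.

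**Common quantities**
- Distance from assumed difference to margin: 1.5 − (−3) = 4.5
- Standard error: 11/√36 = 1.833
- Noncentrality: 4.5/1.833 = 2.4545

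**1. Reproducing the plan's figure (one-sided 0.05, normal approximation)**
- Power = Φ(2.4545 − 1.645) = 79.1%
- n for 80% = [11 × (1.6449 + 0.8416)/4.5]² = 36.94, or 37 rounded up
- Enrolment: 36/(1 − 0.10) = 40, as stated

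The stated power is reproduced to within one percentage point, and the stated n to within one subject.

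**2. Exact t-test, one-sided 0.05 (noncentral t, n − 1 degrees of freedom)**

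| Evaluable n | Power |
|---|---|
| 36 | 77.7% |
| 38 | 79.7% |
| 39 | 80.6% |
| 40 | 81.5% |

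The exact figure at n = 36 is 1.4 points below the normal approximation and 2.3 points below 80%. The exact method first reaches 80% at 39 evaluable subjects.

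**3. If a two-sided 0.05 p-value were used (0.025 in the tail of interest)**
- Normal approximation: 69.0%
- Exact t: 66.5%, with 49 evaluable subjects needed for 80%

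Neither figure could be described as about 80%. The power statement therefore identifies one-sided 0.05 as the level used for sizing.

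**4. Where the choice of p-value would alter the verdict (observed SD 11, n = 36)**
- One-sided: success if the mean is below 1.5 − 1.690 × 1.833 = −1.60
- Two-sided: success if the mean is below 1.5 − 2.030 × 1.833 = −2.22

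Under the design assumptions, the one-sided test succeeds and the two-sided test fails with probability 77.7% − 66.5% = 11.2%.

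**5. Do the documents leave that choice open?** SAP section 8 refers to the hypothesis test. SAP section 7, directly before it, sets out one test, with the alternative at or below the goal, and says that secondary endpoints are not formally tested. A p-value for that alternative comes from the lower tail. A mean significantly above 1.5 lies in the null region, so its lower-tail p-value is close to 1. For example, a true change of +6 lies 4.5 above the margin, so a two-sided test would give p < 0.05 in the harmful direction 66.5% of the time. The stated alternative does not allow that to be called a rejection of the null.

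**The case for a change.** The strongest case for acting is that the intent has to be inferred. The success sentence and the software instruction are where a programmer looks, and neither gives a side, a sides option or a confidence level. A two-sided p-value taken from the output by mistake would cost about 11 points of power and could reverse the verdict for an observed mean between −2.22 and −1.60. Pinning this down costs a few words. The stated power is also above the computed value at n = 36 under both methods.

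Part of this stands. The words are missing, and adding them would be tidy. But the inference is not a close call: four statements of the hypotheses, the description of the sized test and the power figure all point to a lower-tailed test at 0.05. Naming a SAS procedure without listing its options does not mean that the two-sided value will be used, and the documents do not say so. The −2.22 to −1.60 band also assumes that the observed SD is 11.

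On power, the difference between 79.1% and 77.7% is one of method, and the plan claims only an approximate value. Even a reader who insists on the exact figure would not change the design, because the 40 enrolled give between 77.7% (36 evaluable) and 81.5% (all evaluable).

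**Conclusion.** No change to the plan follows. The power claim is a fair rounding: 79.1% by the normal approximation and 77.7% by the exact t-test at one-sided 0.05 with 36 evaluable subjects, given a true difference of −3 and an SD of 11. The side of the test is not named, but the written hypotheses fix it. An analyst following them would run the lower-tailed t-test against 1.5 at 0.05, which is equivalent to requiring the upper limit of the two-sided 90% confidence interval to lie below 1.5. The 66.5% power, the need for 49 subjects and the prospect of a harmful result counting as success all depend on a two-sided reading that the documents do not support. This is missing detail that a competent analyst fills in the same way the plan was sized.

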## 12.3. Additional Analyses

Additional study analyses are possible and may be performed.

## 13. Reports and Publications

### 13.1. Interim Report

An interim report will not be issued during the conduct of this study

### 13.2. Final Report

The final report will be compiled by Solvay Dental 360™ or Sponsor Representative and reviewed, approved and signed off by the Principal Investigator. The Principal Investigator shall submit a final report to the IRB as per local policy and procedures.

### 13.3. Publications

Details of publications will be addressed in each Clinical Investigation Agreement.

## 14. Ethical Considerations

### 14.1. Institutional Review Board Approval

Prior to the initiation of this study, the Principal Investigator must submit the Protocol, patient information sheet, patient consent form and any other documents as may be required to the appropriate IRB for review and approval. The Principal Investigator, and any other member of the investigative team, if a member of the IRB, must not participate in the decision-making. A signed and dated letter granting approval must be provided to Solvay Dental 360™ prior to the initiation of the study. A list of the members of the IRB reviewing this Protocol will be requested.

### 14.2. Informed Consent and Patient Information

The Principal Investigator must explain to each patient the nature of the study, including any risks and benefits, its purpose and procedures, and expected duration of involvement in the study. Each patient must be informed that participation in the study is voluntary and non-participation will not affect his/her right to the most appropriate treatment or affect the doctor/clinician-patient

relationship. Patients have full rights to withdraw from the study at any time, irrespective of their initial consent.

Each subject must also give their permission for representatives of the Sponsor, auditor and regulatory authorities to review their hospital records for the purposes of source data verification.

The principal investigator(s) at each center will ensure that the subject is given full and adequate oral and written information about the nature, purpose, possible risk and benefit of the study. Informed consent process will be conducted in accordance with Code of Federal Regulations Title 21. Subjects must also be notified that they are free to discontinue from the study at any time. The subject should be given the opportunity to ask questions and allowed time to consider the information provided.

The subject's signed and dated informed consent must be obtained before conducting any procedure specifically for the study. The principal investigator(s) must store the original, signed Informed Consent Form in the subject's medical record. A copy of the signed Informed Consent Form must be given to the subject.

### **14.3. Subject Confidentiality**

Subject Confidentiality will be maintained throughout the study, in a way that ensures the information can always be tracked back to the source data. For this purpose a unique identification code (ID number and patient name code) will be used that allows identification of all data reported for each patient. Subject anonymity will be guaranteed and all documentation relating to a subject will be kept in a secure location.

### **14.4. Declaration of Helsinki**

This study will be conducted in accordance with the relevant articles of the Declaration of Helsinki as adopted by the 18th World Medical Assembly in 1964 and as revised in Tokyo (1975), Venice (1983), Hong Kong (1989), South Africa (1996) and Edinburgh (2000) Washington (2002), Tokyo (2004) and Seoul (2008).

### **14.5. Insurance**

All research subjects enrolled in this study are covered by general liability insurance.

## **15. Regulatory Requirements**

This is a post-marketing surveillance study with a FDA clearance and CE marked device approved for this indication, hence, this study does not require submission to the Regulatory Authority.

## **16. Good Clinical Practice Compliance**

This study will be conducted in accordance with the principles of the European Standard EN ISO 14155:2011 Clinical Investigation of Medical Devices for Human Subjects – Good Clinical Practice.

### **16.1. Study Personnel and Responsibilities**

Before a subject's enrollment in the study and any study-related procedures are undertaken the following should be fulfilled:

- Signed Clinical Study Protocol and other agreements
- Approval of the study, investigator and Informed Consent by the IRB
- Collection of study required documents
- Formal written approval by NAMSA

## 16.2. Monitoring

Before first subject is recruited into the study, a representative from the Sponsor or Sponsor's representative will visit the clinical study site to:

- Determine the adequacy of the facilities
- Discuss with the investigator(s) (and other personnel involved with the study) their responsibilities with regard to protocol adherence, and the responsibilities of the Sponsor or Sponsor's designee.

The monitor (Sponsor or designee) will be responsible for securing the compliance of the Principal Investigators to the signed agreement, the study Protocol and all applicable national regulations, guidelines and standards in the country where the study is being conducted.

During the study, the monitor will have regular contact with the study site, including regular monitoring visits to:

- Provide information and support to the investigator(s)
- Confirm that facilities remain acceptable
- Confirm the study team is adhering to the protocol and that data are being accurately recorded in the eCRFs
- Perform source data verification (a comparison of the data in the eCRFs with the subject's medical records at the hospital or practice, and other records relevant to the study). This will require direct access to all original records for each subject (e.g., clinic charts)

The Principal Investigator will allow the study monitor to inspect all electronic Case Report Forms and the subject's clinic records and/or original hospital medical records at these visits. These visits are for the purpose of verifying adherence to the Protocol and the completeness and accuracy of the data being entered on the electronic Case Report Forms.

The planned extent of study monitoring and source data verification (SDV) is detailed in the monitoring plan.

A Principal Investigator found not be in compliance will receive telephone and/or written notification of the deficiency, which will include a request that deviation be corrected immediately.

